In Stage 1, subjects will be randomly assigned to receive two experimental psychotherapy sessions assisted by either active placebo MDMA (3 subjects) or full dose MDMA (5 subjects). Subjects who receive the active placebo dose of MDMA will be offered the option to enroll in the open-label Stage 2 unless they meet any exclusion criteria for study participation. In Stage 2, subjects will receive full dose MDMA and the experimental sessions will otherwise follow the same sequence of events after a single preparatory session. (See Table 3 Time and Events)

All outcome measures will be assessed by a blinded independent rater. The independent rater will assess PTSD symptoms with the CAPS and PDS, quality of life with the GAF, symptoms of depression with the BDI-II, and sleep quality with the PSQI. The subjects will complete the PDS, a self-report measure of their PTSD symptoms, to provide correlations with measures administered by the independent rater. The PDS will be completed at baseline, during every third integrative session after an experimental session, and at the end of each Stage. Baseline assessments will be compared with assessments made in Stage 1.

All subjects will complete a follow-up occurring 2 months after their last experimental session in Stage 1 and Stage 2, if applicable. The blind will be broken for all subjects in Stage 1 after completing this assessment. In addition all subjects will complete a visit 12 months after their final experimental session where outcome measures and a questionnaire on any lasting benefits or harms of the treatment will be administered.

At each visit with the therapists, the subject's general wellbeing and suicidality will be assessed with the Columbia Suicide Severity Rating Scale (C-SSRS). Adverse Events and Concomitant Medications will be collected as described in Section 8.5 and 9.0 of the protocol.

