4.1 Planned Duration of Study

Subjects enrolled in this study will fall into two categories that will determine the duration of the study. These include screening and the follow-up portion of the study.

- Open-label lead-in and Stage 1 only subjects: 14 months
- Stage 1 subjects who continue to Stage 2: 18 months

Table 2. Time & Events MP9 Stage 1	Screen/Baseline	Preparatory	Experiment	tal Session 1	Experimental Session 2		End of Stage 1
Visit #	Prior to Enrollment	V1, 2, 3	V4	V5, 6, 7	V8	V9, 10, 11	V12
Type of Visit	Baseline Screening may take place over more than one day up to one month prior to Visit 1	Preparatory Sessions	Experimental Session 1	Integrative Sessions	Experimental Session 2	Integrative Sessions	Follow-Up & Outcome
Visit Timing or Study day or Window		Approx. 1 week apart	3-5 weeks post V1	Approx. 1 week apart A	3-5 weeks post V4	Approx. 1 week apart ^A	May happen over more then 1 day. 2 months post V8
Informed Consent	X						
Medical/Psychiatric History	X						
General Physical Exam, ECG	X						
Brief Neurological Exam	X						
SCID	X						
Clinical Lab Tests, w/ HIV test	X						
Collect Concomitant Medication		X	X	X	X	X	X
Medication Taper (if applicable)	**	X	**		***		
Drug Screen	X		X		X		
Pregnancy Screen (if applicable)	X		X		X		
CAPS, GAF, BDI -II, PSQI (with Ind. Rater)	X						X
Study Enrollment after meeting I/E		X ^B					
Record to Audio/Video		X	X	X	X	X	
General Well-Being		X	X ^D	X	X D	X	X
Obtain Container Assignment from Randomization Program			X ^C		X ^C		
C-SSRS	X	X^{H}	X D, E, F	X ^J	X D, E, F	X ^J	X
Administer IP Drug + Therapy			X		X		
Monitoring of BP, Pulse and Temp.			X		X		
SUD			X ^{E, G}		X ^{E, G}		
Beliefs of Condition Assignment				Χ ^I		Χ ^I	
Overnight Stay			X		X		
PDS	X			X ^N		X ^N	X
Integrative Therapy Session				X		X	
7 days Integrative Telephone Contact				X ^J		X ^J	
AEs Requiring Medical Attention			X	X	X	X	X
Spont. Reactions and all AEs			X^{K}	X^{K}	X^{K}	X^{K}	
AEs related to changes in psychiatric status or withdrawal		X	X	X	X	X	X
Serious Adverse Events		X	X	X	X	X	X
Unblinding							X^{L}
RRPQ							X^{M}
Issue Memory Aid Card							X^{M}
	. D 0 1 177 1 1 0 1 1 1	241		1 1 61		E 1 1 1 1	

Table 3. Time & Events MP9 Stage 2	Preparatory	Experimen	Experimental Session 1 Experimental Session 2		ental Session 2	End of Stage 2		Long Term Follow-Up
Visit #	V13*	V14	V 15, 16, 17	V18	V 19, 20, 21	V22		1 Year Follow-up

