5.2.7 Evaluation at End of Stage 1 and Unblinding (Visit 12)

The final evaluation in Stage 1 will occur two months after the second experimental session. This visit will consist of two meetings that may be completed on separate days, one with the independent rater and the other with the therapists.

- a. Subjects will meet the independent rater for at least an hour and a half.
- b. The blinded independent rater will administer:
 - CAPS to assess PTSD symptoms
 - PDS to assess self-reported PTSD symptoms
 - BDI-II to assess depression symptoms
 - GAF to assess general psychological function
 - PSQI to assess sleep quality
- c. The blinded independent rater will provide their belief of the subject's condition.
- d. After completing all assessments and measures with the independent rater, the subject will meet with the therapists for approximately 30 minutes.
- e. The therapists will assess suicidality with the C-SSRS.
- f. General wellbeing will be assessed.
- g. The blind will be broken for the subject's condition assignment. The independent rater will remain blind to condition assignment at this time.
- h. If the subject has received active placebo dose MDMA in Stage 1, the therapists will discuss enrollment in Stage 2. (See section 5.2.8)
- i. If the subject has received full dose MDMA in Stage 1 or the open label lead-in, or they elect not to participate in Stage 2, they will complete the Responses to Research Participation Questionnaire (RRPQ) and continue on to the 12-month Follow Up visit and study termination.
- j. Subjects who are not enrolled in Stage 2 may return to taking psychiatric medications if necessary.
- k. Subjects not enrolled in Stage 2 will receive a memory aid card for use between

this visit and the 12-month follow up. Subjects will use this card to record AEs, medications, and changes in psychiatric status that they will be asked about at the termination visit. Memory Aids will not be collected.

1. AEs and medications will be collected as described in Sections 8.5 and 9.0 of the protocol.

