8.0 Adverse Events

8.1 Adverse Events

An adverse event (AE) is defined as any untoward or unfavorable medical occurrence in a clinical research study participant, including any abnormal sign (e.g. abnormal physical exam or laboratory finding), symptom, or disease, temporally associated with the participants' involvement in the research, whether or not considered related to participation in the research. This definition includes concurrent illnesses or injuries and exacerbation of pre-existing conditions.

An *unexpected adverse event* is one that is not listed in the current Investigator's Brochure or an event that is by nature more specific or more severe than a listed event.

All AEs will be monitored by the therapists until resolution or, if the AE becomes chronic, a cause identified. If an AE is unresolved at the conclusion of the protocol, a clinical assessment will be made by the investigator and/or Medical Monitor as to whether continued follow-up of the AE is warranted.

The severity of events reported on the "Adverse Events" CRF will be determined by the investigator as:

- · Mild: No limitation in normal daily activity
- · Moderate: Some limitation in normal daily activity
- · Severe: Unable to perform normal daily activity

The relationship of the study treatment to an AE will be determined by the investigator based on the following definitions:

1. Not Related

The AE is not related if exposure to the investigational product has not occurred, or the occurrence of the AE is not reasonably related in time, or the AE is considered unlikely to be related to use of the investigational product, i.e. there are no facts (evidence) or arguments to suggest a causal relationship, or the AE is more likely related to the subject's pre-existing condition.

2. Possibly Related

The administration of the investigational product and AE are considered reasonably related in time and the AE could be explained by causes other than exposure to the investigational product.

3. Probably Related

Exposure to the investigational product and AE are reasonably related in time and the investigational product is more likely than other causes to be responsible for the AE, or is the most likely cause of the AE.

The relationship of the study treatment to an AE will be determined by the investigator.

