A =First Integrative session is 1 day after Exp. session B =Only on Visit 1 C = At least 24 hrs prior to exp. session D =Approximately 6 hours post MDMA E =At the beginning of the session F =As needed G =Approximately every 60 minutes H=Given on 2nd preparatory session only (V2) I= At 1st integrative visit after each Exp. Session for subjects & therapists and at V12 for the independent rater J = For 7 days post Exp. Session, CSSRS D2 and D7 of calls only, General well being for all 7 days K= Spontaneously reported reactions will be collected on the day of MDMA administration and for seven days after each Exp. Session. L= Determine after completion: Go on to Long-term follow up or Stage 2 M= Only for subjects not going to Stage 2 N= Subjects will complete PDS on third integrative session only

Table 3. Time & Events MP9 Stage 2	Preparatory	Experimental Session 1		Experimental Session 2		End of Stage 2		Long Term Follow-Up
Visit #	V13*	V14	V 15, 16, 17	V18	V 19, 20, 21	V22	1	1 Year Follow-up
Type of Visit	Preparatory Session	Experimental Session 1	Integrative Sessions	Experimental Session 2	Integrative Sessions	Follow-Up & Outcome		Follow-Up & Outcome
Visit Timing or Study day or Window	Within 1 month of V12*	1 week post V13	Approx. 1 week apart ^A	3-5 weeks post V14	Approx. 1 week apart ^A	May happen over more then 1 day. 2 months post V17	0	May happen over more then 1 day. One Year After V8 or V17
Confirm Informed Consent	Х						e	
Confirm Inclusion/Exclusion	X						tag	
Entry into Stage 2	Х						Ś	
Collect Concomitant Medication	Х	Х	Х	Х	Х	Х	6	Х
Record to Audio/Video	Х	Х	Х	Х	Х		e 1	
General Well-Being	Х	X ^B	Х	X ^B	Х	Х	tag	Х
Drug Screen		Х		Х			Š	
Pregnancy Screen (if applicable)		Х		Х			fteı	
CAPS, GAF, PSQI, BDI-II (with Ind. Rater)	Use V12*					Х	0.8	Х
C-SSRS	X	X ^{B, C, D}	Х	X ^{B, C, D}	Х	Х	dn	Х
Administer IP Drug + Therapy		Х		Х			M	
Monitoring of BP, Pulse and Temp.		Х		Х				
SUD		X ^{C, E}		X ^{C, E}			\mathbf{F}_{0}	
Overnight Stay		Х		Х			E	
PDS	Use V12*		X ^H		\mathbf{X}^{H}	Х	ler	Х
Integrative Therapy Session			Х		Х		ြည	
7 days Integrative Telephone Contact			X ^F		X ^F		10	
AEs Requiring Medical Attention	Х	Х	Х	Х	Х	Х		
Spont. Reactions and all AEs		X ^G	XG	X ^G	X ^G			
AEs related to changes in psychiatric status or withdrawal	Х	Х	Х	Х	Х	Х		Х
Serious Adverse Events	Х	Х	Х	Х	Х	Х		Х
RRPQ						Х		
Issue Memory Aid Card						X		
Follow up Questionnaire								Х
Termination Visit								Х

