9.9.4 Safety Analyses

The primary measure of safety will be the reporting of adverse events. The Adverse events considered are Treatment Emergent Adverse Events (TEAE) defined as those AE's that occurred after dosing and existing medical history diagnoses that worsened during the study. Verbatim terms on case report forms will be mapped to preferred terms and system organ classes using the MedDRA dictionary. For incidence reporting if a subject has more than one AE mapped to the same preferred term, that AE will be reported only once using the highest severity and closest relationship to study drug. Subject incidence of AEs will be displayed by treatment group by stage and by system organ class. AEs will also be summarized by severity and relationship to study drug. Subject incidence of SAEs by treatment group by stage will also be displayed. In addition to the listing of all AEs, a listing of SAEs and a listing of AEs leading to discontinuation of study drug will be included.

Summary tables of frequency listings of commonly reported AEs (Spontaneously Reported Reactions) mapped to preferred terms will be displayed during and after each experimental session by Stage 1 treatment group.

Columbia Suicide Severity Rating Scale (C-SSRS)

Suicidal ideation and behavior will be summarized according to suggestions made in the Columbia-Suicide Severity Rating Scale Scoring and Data Analysis Guide [2]. A positive response for suicidal ideation is counted when a subject answers "yes" to any one of the five suicidal ideation questions (Categories 1-5) on the C-SSRS, i.e. a score > 0 for suicidal ideation score. Serious suicidal ideation is a suicidal ideation score of 4 or 5. A positive response for suicidal behavior occurs when a subject answers "yes" to any one of the five suicidal behavior questions (Categories 6-10) on the C-SSRS, i.e. a score > 0 for suicidal behavior score. The number and percent of positive responses of Positive Ideation, Serious Ideation, and Positive Behavior will be tabulated by Stage I treatment group and time period. Compare lifetime serious suicidal ideation and positive behavior frequencies to cumulative frequencies anytime during the study until end of Stage 1 and Stage2.

Subjective Units of Distress (SUD)

Descriptive statistics for SUD scores will be calculated by Stage 1 treatment group and time period with counts and percentages.

Vital signs

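### At Visit 12 the protocol lists unblinding before adverse event collection, and nothing requires events newly reported there to be elicited and rated first

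*Protocol*

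**What the plan says.** Protocol 5.2.7 splits V12 into a meeting with the independent rater and a later one with the therapists. The therapist meeting is listed as: suicidality scale (e), wellbeing (f), unblinding (g: "The blind will be broken for the subject's condition assignment"), discussion of Stage 2 (h), research participation questionnaire, RRPQ (i), return to psychiatric medication (j), memory aid card (k). The last item is "AEs and medications will be collected as described in Sections 8.5 and 9.0 of the protocol". Protocol 5.4 states that the subject and therapists, but not the independent rater, learn the assignment at this point.

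Two general statements bear on the order. Protocol 4.0, speaking of the 2-month follow-up, says "The blind will be broken for all subjects in Stage 1 after completing this assessment". Protocol 5.3 has blinded personnel carry out all evaluations in the randomised part until each subject's blind is broken.

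On the use of the data, Protocol 8.1 has the investigator grade severity and says "The relationship of the study treatment to an AE will be determined by the investigator". SAP 9.9.4 says "The primary measure of safety will be the reporting of adverse events" and summarises AEs by treatment group, severity and relationship to study drug.

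**The concern.** Severity and relatedness are judgements, and eliciting AEs depends on how hard one asks. If subject and therapists already know the dose, expectation can raise reporting and attribution in the full-dose arm and lower them in the 25 mg arm. The rater's scales, the suicidality scale and wellbeing all sit before item g; AE collection is the safety item listed after it.

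V12 is also the first scheduled visit for some weeks, so events from that gap may first be mentioned there. The memory aid card is issued only at V12, so it cannot support recall over the gap. Psychiatric-status events matter most in this population and rest largely on self-report and judgement. The SAP does not separate AEs first recorded after unblinding, so any such bias could not be identified in the tables.

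**Working it through.** The plan gives no figure for this point. The check has two parts: the order of steps, and the calendar time involved.

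**Order of steps.** Items d to i of Protocol 5.2.7 form a sequence. Item d follows completion of the rater's assessments, and items h and i depend on the dose having been revealed at g. The AE item comes after all of these. Section 4.0 unblinds after the 2-month assessment, and 5.3 keeps evaluators blinded until then, but neither says whether AE collection is part of what must come first. Footnote L to Table 2, as printed in the SAP, only routes subjects to follow-up or Stage 2 after completion.

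**Calendar time.** Inputs, with V8 as day 0:

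- V12: "The final evaluation in Stage 1 will occur two months after the second experimental session" (Protocol 5.2.7). Two months is taken as 60 days, with 56 and 61 as alternatives (assumption).
- V8: "3-5 weeks post V4" (Protocol Table 2), so V4 to V8 is 21 to 35 days.
- V9: "First Integrative session is 1 day after Exp. session" (SAP Table 2, footnote A), so day 1. V10 and V11 follow about a week apart, so V11 is about 1 + 7 + 7 = day 15. Day 21 is used as a late case (assumption).

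Formula: share = (V12 day − V11 day) / (V4-to-V8 days + V12 day).

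| V4 to V8 | V12 day | V11 day | Gap V11 to V12 | V4 to V12 | Share |
|---|---|---|---|---|---|
| 21 | 60 | 15 | 45 | 81 | 56% |
| 28 | 60 | 15 | 45 | 88 | 51% |
| 35 | 60 | 15 | 45 | 95 | 47% |
| 35 | 56 | 21 | 35 | 91 | 38% (lowest) |
| 21 | 61 | 15 | 46 | 82 | 56% (highest) |

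**Which events fall in that gap.** Under Protocol 8.5, all AEs are collected only on the dosing day and for seven days after each session: 2 × (1 + 7) = 16 days. The second window closes at day 7 after V8, before V11, and is covered by blinded visits and daily calls. Between V11 and V12 the protocol still collects serious AEs, events needing medical attention, psychiatric-status AEs and AEs leading to withdrawal. Serious AEs are reported within 24 hours of the investigator's awareness. A subject who withdraws before V12 is handled under Protocol 5.4, with the cause recorded then. What remains to be first heard at V12 is mainly medically attended and psychiatric-status AEs.

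**Scale of one event.** With 5 and 3 subjects, one subject is 1/5 = 20% or 1/3 = 33% of an arm. This describes arms of this size; it does not estimate what the ordering does.

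**The case against.** The strongest reply is that list position is not a timetable. The AE line is a standing cross-reference at or near the end of most visit lists. In Protocol 5.2.3 it follows the therapists' departure, and in 5.2.4 it follows the ride home; nobody would read those lists as an order to collect AEs afterwards. Table 2 prints the AE rows above the unblinding row, and section 4.0 can be read as unblinding after the whole visit. This stands as far as it goes: the protocol does not mandate unblinded AE collection. It does not settle the matter, because in 5.2.7 the unblinding step sits inside a genuine sequence and no sentence puts AEs ahead of it.

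A reader might infer that therapists will assign relatedness with the dose known. The documents do not say so. Section 8.1 gives that task to the investigator. The abbreviations list offers therapists as an example of a Clinical Investigator, while section 6.2.3 names investigator and therapists separately. Rating by an unblinded therapist is therefore possible but not stated. Unblinded elicitation is more direct, since section 12.0 has therapists record AEs.

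It is also fair that the suicidality scale and wellbeing precede item g, so some psychiatric events would surface under the blind even on a strict reading, and that extra sessions or subject-initiated contact may bring out others earlier.

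Finally, one might want the RRPQ moved to V12 for everyone, because Stage 2 entrants complete it after open-label full dose while SAP 9.9.3.1 displays it by Stage 1 condition. Protocol 5.1.1 places it at the final visit by design and says that it is not an outcome measure, so the documents do not support calling its timing an error.

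**Conclusion.** The gap in the text is real and limited. As listed, V12 allows AEs newly reported at that visit to be elicited, and possibly rated for severity and relatedness, after subject and therapists know the dose; sections 4.0 and 5.3 imply the opposite intent without securing it. The period concerned is about 45 days on the central assumptions (35 to 46 across the cases), or 38% to 56% of V4 to V12.

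That range should not be read as half of the AEs. It is calendar time in which only restricted categories are collected, and the documents give no basis for estimating how many events would be affected. The conclusion rests on V11 falling at day 15 to 21 after V8, on two months meaning 56 to 61 days, and on sites treating the list as an order of work. The independent rater stays blind, so the primary CAPS comparison is not touched. The safety tables are descriptive, but AE reporting is the SAP's primary safety measure, and the bias can be prevented at almost no cost and cannot be removed afterwards.

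**What to change.** In Protocol 5.2.7, move AE and medication collection to between items f and g, and require severity and relatedness for every event reported up to that point to be recorded and dated before the blind is broken. Add to Table 2 footnote L a line such as: *unblind only after AEs and medications for this visit, with severity and relatedness, have been recorded and dated*. Make 4.0 and 5.3 agree by stating that AE collection and rating belong to the assessment that precedes unblinding.

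The cost is a reordering within a meeting of about 30 minutes, with no new measure or visit. If the investigator who rates relatedness is not one of the therapists, that person must give the rating before item g.

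Leave the RRPQ schedule as it is. At most, add a note in SAP 9.9.3.1 that responses from Stage 2 entrants were given after open-label full dose.

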5.2.8 Open Label Stage 2 for Active Placebo Subjects

- a. Subjects will be reminded that participation in Stage 2 is voluntary and optional.
- b. Subjects who elect to enroll in Stage 2 will undergo the same course of therapy and evaluation as in Stage 1, but with full dose MDMA during two experimental sessions.
- c. Assessment of PTSD symptoms at the end of Stage 1 will serve as baseline assessments in Stage 2.
- d. If the start of Stage 2 is delayed for more than 30 days from the time of the last CAPS in Stage 1 to the first preparatory session in Stage 2 (Visit 13), the independent rater will re-administer the CAPS, PDS, BDI-II, GAF and PSQI, and these scores will be used as the baseline for comparison to assessment at the end of Stage 2.
- e. Subjects entering Stage 2 will meet with both therapists for a single review and preparatory psychotherapy session (Visit 13).
- f. Subjects will receive two open-label MDMA-assisted therapy sessions (V14, 18).
- g. Subjects will have the same sequence of sessions and integrative therapy as in Stage 1. Visits will be scheduled consecutively according to the Time and Events Table 3.
- h. Subjects will complete the PDS on the third integrative session.
- i. The same safety measures will be administered during Stage 2, including C-SSRS before, during and after each open-label session, vital signs and SUD during each open-label session.
- j. Spontaneously reported reactions, AEs and Medications will be collected and reported as described in Section 8.5 and 9.0 of the protocol.

5.2.9 Evaluation at the End of Stage 2

Treatment effects will be assessed at the end of Stage 2. This visit will consist of two meetings that may be completed on separate days, one with the independent rater and the other with the therapists.

- a. Subjects will meet the independent rater for at least an hour and a half.
- b. The blinded independent rater will administer:
 - CAPS to assess PTSD symptoms
 - PDS to assess self-reported PTSD symptoms
 - BDI-II to assess depression symptoms
 - GAF to assess general psychological function
 - PSQI to assess sleep quality

- c. After completing all assessments and measures with the independent rater, the subject will meet with the therapists for approximately 30 minutes.
- d. The therapists will assess suicidality with the C-SSRS.
- e. General wellbeing will be assessed.
- f. The subject will complete the Responses to Research Participation Questionnaire (RRPO).
- g. Subjects may return to taking psychiatric medications if necessary.
- h. Subjects will receive a memory aid card for use between this visit and the 12-month follow up. Subjects will use this card to record AEs, medications, and changes in psychiatric status that they will be asked about at the termination visit. Memory Aids will not be collected.
- i. AEs and medications will be collected as described in Sections 8.5 and 9.0 of the protocol.

